2.3 Patient demographics and other baseline characteristics

The FAS will be used for all patient demographic and baseline characteristic summaries and listings.

Basic demographic and background data

All demographic and baseline disease characteristics data will be summarized and listed by cohort. Categorical data (e.g. gender, race, ethnicity, ECOG performance status) will be summarized by frequency count and percentages. Continuous data (e.g. age, weight, height, BMI) will be summarized by descriptive statistics (as defined in [Section 2.1](#)).

Diagnosis and extent of cancer

Descriptive statistics and frequency counts and percentages will be tabulated by cohort, as appropriate, for diagnosis and extent of cancer based on the data collected on the electronic Case Report Form (eCRF) including: primary site of cancer, tumor histology/cytology, histological grade, time (in months) since initial diagnosis of primary site, stage at initial diagnosis, time (in months) from initial diagnosis to first recurrence/progression, time (in months) since most recent relapse/progression, current extent of disease (metastatic sites), number of metastatic sites at baseline, types of lesions (target and non-target lesions) at baseline, number of target lesions at baseline, and disease burden at baseline for target lesion (based on the data collected on the RECIST eCRF page).

Medical history

Medical history and ongoing conditions, including cancer-related conditions and symptoms will be summarized and listed by cohort. Separate summaries will be presented for ongoing and historical medical conditions. The summaries will be presented by primary system organ class and preferred term. Medical history and current medical conditions are coded using the Medical Dictionary for Regulatory Activities (MedDRA) terminology.

Prior anti-cancer therapy

Prior anti-neoplastic (anti-cancer) therapy will be listed in three separate categories by cohort: 1. medications, 2. radiotherapy, and 3. surgery.

The number and percentage of patients who received any prior anti-neoplastic medications, prior anti-neoplastic radiotherapy or prior anti-neoplastic surgery will be summarized by cohort.

Prior anti-neoplastic medications will be summarized by chemotherapy (medication) setting, other therapy (medication) setting, number of prior regimens of anticancer medications and

prior anticancer medications. Prior antineoplastic medications will also be summarized by ATC class, and preferred term. The medication therapy type of any combination therapy will be classified based on the following order: immunotherapy, chemotherapy, biologic therapy (other than immunotherapy), targeted therapy, hormonal therapy. For example, a combination therapy of chemotherapy and immunotherapy will be classified as 'immunotherapy'.

Prior anti-neoplastic systemic medications (any line, 1st line, 2nd line) will be summarized by line: single agent chemotherapy, Platinum based chemotherapy, immunotherapy.

For radiotherapy, time since last radiotherapy, locations and setting of last therapy will be summarized. For prior surgery, time since last surgery, procedure and residual disease of last therapy will be summarized.

2.4 Protocol deviations

In addition to the pre-defined standard PD terms, new protocol deviations and the corresponding relationship (health status related, lockdown/quarantine of patient, site issues, patient concerns, etc.) to the COVID-19 pandemic in line with "FDA Guidance on Conduct of Clinical Trials of Medical Products during COVID-19 Public Health Emergency" ([March 2020](#)) and "Guidance on the management of clinical trials during the COVID-19 (coronavirus) pandemic" ([February 2021](#)) from EMA were defined.

Frequency counts and percentages of patients in the FAS with any protocol deviations (related to study inclusion/exclusion criteria, conduct of the trial, patient management or patient assessment) will be tabulated by deviation category and cohort, broken down by COVID-19 relationship (COVID-19 related PDs or not). Major protocol deviations will be tabulated separately by cohort. A cross-tabulation of COVID-19 related protocol deviations vs. corresponding COVID-19 situation will also be produced by cohort. All protocol deviations will be listed by cohort.

2.5 Patient disposition

The FAS will be used for the patient disposition summary tables by cohort. The FAS will be used for the listings by cohort.

The following will be tabulated:

- Number (%) of patients who are still on-treatment (based on the absence of the 'End of Treatment Phase Disposition' page);
- Number (%) of patients who discontinued treatment (based on completion of the 'End of Treatment Phase Disposition' page with date of discontinuation and reason of discontinuation/ 'Subject Status' entered);
- Number (%) of patients who entered post treatment efficacy follow-up (based on 'Next Phase Entered' is 'Post-treatment follow-up' on the 'End of Treatment Phase Disposition' page for patients who discontinued treatment);
- Number (%) of patients who entered survival follow-up (based on 'Next Phase Entered' is 'Survival follow-up' on the 'End of Treatment Phase Disposition' page for patients who discontinued treatment);

- Number (%) of patients who discontinued from study (based on ‘Will subject continue into the next phase of the trial’ is ‘No’ as entered on the ‘End of Treatment Phase Disposition’ page for patients who discontinued treatment);
- Primary reasons for study treatment discontinuation (based on discontinuation reasons entered under ‘Subject Status’ in the ‘End of Treatment Phase Disposition’ page);
- Number (%) of patients who are still in the post-treatment study phase (based on presence of ‘End of Treatment Phase Disposition’ and absence of ‘Study Phase Disposition’ page);
- Number (%) of patients who discontinued from the post-treatment efficacy follow-up (based on completion of ‘Study Phase Disposition’ page with date of discontinuation and discontinuation reasons entered under ‘Subject Status’);
- Number (%) of patients who entered survival follow-up (based on completion of ‘Study Phase Disposition’ page with date of discontinuation and discontinuation reasons entered under ‘Subject Status’ and ‘Next Phase Entered’ is ‘Survival follow-up’ for patients who discontinued from the post-treatment efficacy follow-up);
- Number (%) of patients who discontinued from study (based on completion of ‘Study Phase Disposition’ page with date of discontinuation and discontinuation reasons entered under ‘Subject Status’ and ‘Will subject continue into the next phase of the trial’ is ‘No’ for patients who discontinued from the post-treatment efficacy follow-up);
- Primary reasons for discontinuation from the post-treatment efficacy follow-up (based on discontinuation reasons entered under ‘Subject Status’ in the ‘Study Phase Disposition’ page).

Note: ‘Study Phase Disposition’ page corresponds to ‘End of Post-Treatment disposition’ CRF page.

2.6 Treatments (study drug, concomitant therapies, compliance)

The Safety Set will be used for all medication data summaries and listings unless otherwise specified.

Study drug and study treatment

Study drug and study treatment both refer to INC280 and will be used interchangeably.

Date of first/last administration of study drug

The date of first administration of study drug is defined as the first date when a non-zero dose of study drug was administered and recorded on the Dosage Administration Record (DAR) eCRF. For the sake of simplicity, the date of first administration of study drug will also be referred to as start date of study drug.

The date of last administration of study drug is defined as the last date when a non-zero dose of study drug was administered and recorded on DAR eCRF. This date will also be referred to as last date of study drug.

Study day

The study day for all assessments (e.g. tumor assessment, death, disease progression, tumor response, performance status, adverse event onset, laboratory abnormality occurrence, vital sign measurement, dose interruption) will be calculated using the start date of study drug as the origin. For assessments occurring after or on the start date of study drug, study day will be calculated as:

Study Day =Event date - start date of study drug + 1.

The first day of study drug is therefore study day 1.

For any assessment or events such as baseline disease characteristics or medical history (e.g., time since diagnosis of disease) occurring prior to the start of the study drug, study day will be negative and will be calculated as:

Study Day = Event date - start date of study drug.

The study day will be displayed in the relevant data listings.

Dose exposure and intensity

Definitions of duration of exposure, cumulative dose, average daily dose, dose intensity (DI), relative dose intensity (RDI), as well as intermediate calculations, include:

- Duration of exposure (days): last date of study drug – first date of study drug + 1 (periods of interruption are not excluded)
- Cumulative dose (mg): total dose of study drug taken by a patient in the study
- Number of dosing days (days): duration of exposure – number of zero dose days
- Average daily dose (mg/day): cumulative dose (mg) / number of dosing days (days)
- DI (mg/day): cumulative dose (mg) / duration of exposure (days)
- RDI (%): $100 \times [\text{DI (mg/day)} / \text{planned dose (800 mg/day)}]$

Note: Because the planned INC280 dose is 800 mg/day, or the planned dose intensity (PDI) is 800 mg/day, RDI (%) can be calculated by $100 \times \text{DI}/\text{PDI}$ and simplified as shown above.

Duration of study exposure to study drug, cumulative dose, average daily dose, DI and RDI will be summarized by cohort. In addition, the duration of exposure to study drug will be categorized into time intervals and frequency counts and percentages of patients with exposure in each time interval will be presented. Frequency counts and percentages of patients who have dose changes, reductions or interruptions, and the corresponding reasons, will be summarized by cohort.

An analysis of time to first interruption (in weeks) will be presented based on simple descriptive statistics (not using time-to-event methods).

Time to first interruption is the time from date of first administration of study drug to the first date when a zero dose of study drug is recorded on the DAR eCRF, expressed in weeks. Listings of all doses of the study drug along with dose change and dose interruption reasons will be produced by cohort.

Section 4.5 provides further details on the definition of dose changes and interruptions.

Concomitant therapy

Concomitant therapies are defined as any medications (excluding study drug, prior antineoplastic treatments and blood transfusions), surgeries or procedures (including physical therapy) administered in the study and are recorded in the Prior and Concomitant Medications and the Surgical and Medical Procedures eCRF, respectively.

Concomitant medications will be coded using the WHO Drug Reference Listing (WHO DRL) dictionary that employs the WHO Anatomical Therapeutic Chemical (WHO ATC) classification system. Surgeries or procedures will be coded using the Medical Dictionary for Regulatory Activities (MedDRA) terminology. All summaries will be tabulated using frequency counts and percentages.

Concomitant therapies will be summarized by ATC class, preferred term and cohort. Surgical and medical procedures will be coded using MedDRA and summarized by SOC and preferred term. These summaries will include: 1) medications starting on or after the start of study drug but starting no later than 30 days after last dose of study drug and 2) medications starting prior to the start of study drug but continuing after the start of study drug.

All concomitant therapies will be listed by cohort. Any concomitant therapies starting and ending prior to the start of study drug or starting more than 30 days after the last date of study drug will be flagged in the listings.

Antineoplastic therapy after discontinuation of study drug

The FAS will be used for all listings and summaries of antineoplastic therapies initiated after discontinuation of study drug. All summaries will be tabulated using frequency counts and percentages by cohort.

Antineoplastic medications initiated after discontinuation of study drug will be summarized and listed by Anatomical Therapeutic Chemical (ATC) class, preferred term and cohort.

Antineoplastic radiotherapy since discontinuation of study treatment will be summarized and listed by setting and cohort.

Antineoplastic surgery since discontinuation of study treatment will be summarized and listed by SOC and preferred term and cohort.

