### 6.3.3 Treatment interruption and treatment discontinuation

If the administration of INC280 is temporarily interrupted for reasons other than toxicity, then treatment with INC280 may be resumed at the same dose. If the treatment with INC280 is withheld due to toxicity, the dose modification guidelines in [Table 6-3](#) should be followed. In any case, scheduled visits and all assessments (including tumor assessments) should continue to be performed, as described in [Table 7-1](#).

If the treatment with INC280 is withheld for more than 21 consecutive days (counting from the first day when a dose was interrupted), then INC280 should be permanently discontinued. Under exceptional circumstance, when the investigator believes that continuing treatment may still derive clinical benefit for the patient, study treatment may be resumed. However, the investigator must discuss and receive approval from Novartis Medical Lead or designee prior to continuing INC280 treatment.

Patients who discontinue the study due to a study drug related AE or an abnormal laboratory value must be followed as described in [Section 6.3.4](#).

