4.5 Dose interruptions and dose changes

This section provides additional details to those included in [Section 2.6](#).

All calculations of dose interruptions and dose changes are based on the dose actually taken by the patient.

An interruption is defined as a 0 mg dose taken on one or more days between two non-zero dosing periods. The last zero dose of INC280 followed by permanent discontinuation are not considered as dose interruption.

What follows defines how dose interruptions will be counted in the case of multiple dose interruptions.

- If an interruption occurs consecutively for at least two days due to the same reason, then it will be counted only once (*example: If the actual dose on days 1-3 is 800 mg and actual dose on days 4-5 is 0 mg and dose interruption on days 4-5 is due to AE, then the total number of dose interruptions is 1*).
- If an interruption occurs consecutively for at least two days due to different reasons, then it will be counted for each reason (*example: If the actual dose on days 1-3 is 800 mg and*

actual dose on days 4-5 is 0 mg and dose interruption on day 4 is due to AE and dose interruption on day 5 is due to dosing error, then the total number of dose interruptions is 2).

- If an interruption occurs for more than one day due to the same reason, but the days are not consecutive, i.e. there is at least one dosing day in between, then each dose interruption will be counted as a different occurrence (*example: if the actual dose on days 1, 3 and 5, is 800 mg and actual dose on days 2 and 4 is 0mg, and dose interruptions on day 2 and 4 are both due to dosing error, the total number of dose interruptions is 2).*

A dose change is defined as a change in dosing from one record to the next, however a dose interruption will not be counted as a dose change.

Dose reductions are a subset of dose changes where the total daily dose is lower than the previous non-zero dose.

Case 1: If a patient did not receive the protocol planned dose for any reason, then this is a dose reduction (400 mg, 800 mg).

Patient ID	Start date	End date	Dose	Regimen	Reason	Reduction (derived)	Comments
0001	22/03/2017	25/03/2017	400	ONCE PER DAY	DOSING ERROR	Y	1 st administration different from protocol planned dose (800 mg)
	26/03/2017	26/05/2017	800	2 TIMES PER DAY			

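### SAP 2.6 times the first interruption from any first zero dose, including terminal zero doses that SAP 4.5 does not count as interruptions

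*SAP*

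**What the plan says.** **Timing rule (SAP 2.6, Dose exposure and intensity).** "Time to first interruption is the time from date of first administration of study drug to the first date when a zero dose" is recorded on the dosing eCRF, expressed in weeks. The summary uses simple descriptive statistics, not time-to-event methods. The same section calls for counts and percentages of patients with interruptions, by cohort, and refers to Section 4.5 for more detail on what an interruption is.

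**Definition (SAP 4.5).** An interruption is a 0 mg dose on one or more days with non-zero dosing before and after it. "The last zero dose of INC280 followed by permanent discontinuation are not considered as dose interruption".

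**Exposure span and dosing days (SAP 2.6).** "The date of last administration of study drug is defined as the last date when a non-zero dose of study drug was administered" and recorded. Duration of exposure runs from first to last such date, with interruptions left in. Then: "Number of dosing days (days): duration of exposure – number of zero dose days". Average daily dose is cumulative dose divided by that number of days.

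**Holds before stopping (Protocol 6.3.3).** "If the treatment with INC280 is withheld for more than 21 consecutive days", permanent discontinuation is the default, with an exception by sponsor approval.

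**The concern.** Sections 2.6 and 4.5 give different answers for a patient who is held and never restarted. Under 2.6 the first zero-dose record fixes a time to first interruption. Under 4.5 that record is not an interruption. A programmer who codes each section as written will produce a timing table and a frequency table with different patients in them.

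The tables describe tolerability. Protocol 10.5.3.5 summarizes tolerability through dose reductions and drug interruptions due to adverse events. Because the timing summary has no censoring, each such patient enters the mean and median directly. That patient's value is in effect the time to stopping treatment, not the time to a temporary hold.

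**Working it through.** The documents state no time to first interruption and no average daily dose, so there is no plan figure to reproduce. The check applies the two definitions to the same dosing history.

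**1. Patient whose only zero dose is terminal.** Assume non-zero dosing on days 1 to L without a gap, then zero-dose records, then permanent stop.
- SAP 2.6: the first zero-dose day is day L + 1, so the interval is (L + 1) − 1 = L days, or L/7 weeks.
- SAP 4.5: no non-zero period follows, so there are 0 interruptions.
- L = 60: 60/7 = 8.6 weeks under 2.6, none under 4.5.
- L = 126: 126/7 = 18.0 weeks under 2.6, none under 4.5.

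The value equals the duration of exposure, L days. SAP 2.6 does not say whether a day is added to this interval. Adding one would raise each figure by 1/7 week and leave the mismatch unchanged.

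**2. Effect on the two tables.** Let m be the number of patients with an interruption under 4.5, and k the number whose only zero doses are terminal. The frequency table counts m. The timing summary, read literally, covers m + k. The documents do not give k.

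**3. Patient with an earlier true interruption.** The SAP 4.5 Case 3 example records both end in a 0 mg record with no later dose shown.
- 0004: first dose 27-Dec-2017, first zero dose 16-Jan-2018, 20 days later.
- 0005: first dose 25-Apr-2016, first zero dose 24-May-2016, 29 days later.

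In each, the first zero dose lies between non-zero periods, so the closing zero doses do not alter the result.

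**4. Case 3 start date.** For 0004 the comment dates the interruption to 15-Jan, when 400 mg was taken. The first zero dose is on 16-Jan. The two dates give 19 and 20 days, and the 0 mg definition in 4.5 agrees only with the later one.

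**5. Average daily dose on two readings.** The dose column is read as mg/day. The SAP does not say that 0004 and 0005 stopped permanently, so they show the arithmetic only.

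| Record | Cumulative dose (mg) | Duration (days) | Zero days inside span | Zero days after span | Inside span only (mg/day) | Every zero day subtracted (mg/day) |
|---|---|---|---|---|---|---|
| 0004 | 25,200 | 43 | 7 | 12 | 25,200/36 = 700.0 | 25,200/24 = 1,050.0 |
| 0005 | 76,800 | 100 | 2 | 5 | 76,800/98 = 783.7 | 76,800/93 = 825.8 |

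The last column exceeds the planned 800 mg/day in both records, although no dose in either record is above 800. That reading therefore cannot be what the term dosing days means.

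**6. Dose intensity.** This is cumulative dose over duration and does not use zero-dose days. For 0004 it is 25,200/43 = 586.0 mg/day, with relative dose intensity 586.0/800 = 73.3%. For 0005 it is 76,800/100 = 768.0 mg/day and 96.0%. Neither depends on the reading.

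**The case against.** **The cross-reference.** SAP 2.6 points to 4.5 for the definition of interruptions, and 4.5 says that it adds detail to 2.6. Read together, the exclusion of terminal zero doses could be taken to govern. This softens the conflict but does not remove it. Section 2.6 states its own explicit end point, the first recorded zero dose, and 4.5 neither restates nor overrides it.

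**Frequency.** Terminal zero-dose records may be few. In the one worked example of permanent discontinuation (4.5, Case 4, patient 0006), the stop is flagged on the last non-zero record and no zero dose follows. The 21-day rule in Protocol 6.3.3 limits withholding but does not say how a final hold is entered. This stands as a limit on size. Section 4.5 nevertheless names such records, so they are expected.

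**A stronger reading.** A reader might infer that average daily dose is also wrong, and inflated in the patients who tolerated the drug least. With 60 days at 800 mg/day and a 21-day terminal hold, subtracting every zero day gives 48,000/(60 − 21) = 1,231 mg/day instead of 800. The documents do not support this as a consequence of the plan. The formula does not say that all zero-dose days are subtracted. Duration is defined with interruptions left in, and the next step removes them, which points to zero days inside the span. The 1,231 figure needs the unnatural reading, an invented patient, and a full 21-day hold entered as zero-dose records.

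**Conclusion.** The timing rule in SAP 2.6 conflicts with the definition in SAP 4.5 and needs correcting. The conflict affects only patients whose first and only zero dose is the terminal one. For them, 2.6 yields a time and 4.5 yields no interruption.

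The size is unknown, because the number of such patients is not in the documents. The conclusion assumes that some terminal holds are recorded as zero doses, as 4.5 implies. The average-daily-dose formula leaves its window unstated but is right on its natural reading, so it does not support a claim that both exposure measures are wrong.

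The severity is minor. Only descriptive exposure summaries are involved. Dose intensity and relative dose intensity, the intensity measures that Protocol 10.3 asks for, are unaffected, as is the primary ORR analysis.

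**What to change.** In SAP 2.6, define time to first interruption as the time from first administration to the first zero-dose day of the first interruption as defined in Section 4.5. State that zero doses after the last non-zero dose do not count, and that patients with no such interruption are left out of this summary.

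Reconcile this with the Case 3 comment in 4.5, which dates an interruption to a half-dose day. As it stands, that comment conflicts with the 0 mg definition, so one start date should be stated for timing purposes.

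As an optional clarification, specify in the dosing-days formula that zero-dose days are counted only between the first and last non-zero dose.

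The cost is one sentence, one reconciled comment and an optional phrase, with the matching programming condition. No new data are needed, and no dose or clinical rule changes.
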